### **12.5 Roll-in Procedures**

Upon completion of the Roll-in procedures at each site (minimum of 150 procedures at each clinical site), summary statistics of Adverse Events (category and sub-category) will be evaluated by the DSMB. The summary statistics listing will have the randomization category, device serial number, device software version, collection volume at time of adverse event, total plasma volume and total collection volume fields hidden from reviewers. If deemed acceptable, the study enrollment will remain unaffected and will continue. Roll-in procedures will be included in the evaluable population. Enrollment will not be paused during the safety evaluation.

### **12.6 Data Safety Monitoring Board Review**

A Data Safety Monitoring Board (DSMB) may conduct one or more safety analyses based on the Criteria for DSMB Review (Section 12.10) to review safety-related data. All members of the DSMB will be external to Fresenius Kabi. The DSMB will meet as required and will monitor the safety of the trial, according to the DSMB charter.

The Criteria for DSMB Review will be shared with the DSMB, which will determine, based on these or alternative criteria that they may independently develop, the safety of continuing with the study. This evaluation will be based on a comprehensive review of the available safety information as the clinical trial progresses. The DSMB may have access to additional information in its review, e.g., from a requested unblinded data review, that may allow them to come to a more informed decision. Their independent assessment will be shared with the sponsor team.

The DSMB will also review data related to the Criteria for DSMB Review, as defined in section 12.10. The DSMB will determine if it is safe to continue the trial or will decide to terminate the study. This decision is binding for the sponsor.

## **12.7 Subject Disposition**

Subject disposition and reasons for study procedure/drug discontinuation will be summarized for inclusion in the final report.

## **12.8 Subject Demographics and Baseline Characteristics**

Subject demographics and baseline characteristics will be collected and summarized for inclusion in the final report.

## **12.9 Protocol Deviations**

A protocol deviation is defined as any change or alteration from the procedure stated in the study plan, consent form or clinical trial materials that were originally provided by the sponsor and approved by the IRB.

All protocol deviations must be reported to Fresenius Kabi through the TrackWise System data files. All deviations, regardless of whether medically justifiable (e.g., the subject's safety), shall be reported. In addition, the qualified healthcare professional is required to adhere to the IRB's reporting requirements for protocol deviations.

Qualified healthcare professionals are required to maintain accurate, complete and current records, including documentation showing the dates of, and reasons for, each deviation from the protocol. Failure to comply with the protocol may result in qualified healthcare professional termination of participation in the clinical trial.

## **12.10 Criteria for DSMB Review**

In addition to safety monitoring after the roll-in procedures, the following criteria for DSMB review will apply for possible study termination due to safety concerns:

### Rule 1: Subject Death

If at any time during the study there are:

- One or more subject deaths reported.

### Rule 2: Occurrence of Severe Hypotensive Events

If at any point in the first 50% of planned procedures, there are:

- 6 or more severe hypotensive events [1.5 (Hypotensive; Severe (With or Without LOC)) or 1.6 (Hypotensive; Injury)] of the IQPP definition.

Within 24 hours of sponsor notification, the DSMB will be notified of the event(s) and perform an unblinded review of the event(s). If the event(s) is determined to be related to

the Investigational Product and affects the safety profile, the study will be put on hold and the information will be transmitted to the FDA immediately.

If the event(s) is determined not to be related to the Investigational Product and has no effect on the safety profile, the study may continue and all DSMB documentation of the event(s) and decision will be immediately transmitted to the FDA for further review.

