For the primary endpoint analysis, individuals will be eligible to donate for a maximum of 8 weeks, a time set to minimize the effect of the date of enrollment on the number of possible procedures per participant. It is estimated that the study will enroll approximately 11,519 subjects, but fewer subjects may be enrolled if the number of procedures per subject is greater than the current estimate. Upon collection of the target number of procedures and analyzing the primary endpoint, an optional extension period may commence, during which only donors who qualify for one or more high risk subgroup (female, weight  $\leq$ 124 lbs,  $\leq$ 20 years of age and First-Time Donor) will be enrolled and undergo on-study collections. Individuals consented prior to the extension period may continue donating during this extension if they qualify for one or more of the relevant subgroups. The purpose of this extension period would be to generate additional data to support the secondary subgroup analysis. Collections during the extension period will not be included in the primary endpoint analysis since it represents a period of biased enrollment. After analyzing the primary endpoint, an optional extension period may commence, during which only donors who qualify for one or more high risk subgroup (female, weight  $\leq$ 124 lbs,  $\leq$ 20 years of age and First-Time Donor) will be enrolled and undergo on-study collections. Individuals consented prior to the extension period may continue donating during this extension if they qualify for one or more of the relevant subgroups. The purpose of this extension period would be to generate additional data to support the secondary endpoint subgroup analysis. Collections during the extension period will not be included in the primary endpoint analysis since it represents a period of biased enrollment.

Plasmapheresis subject evaluations will be completed pre-procedure. Other parameters, including adverse events, will be collected during and/or post-procedure (See section 7 - Study Procedures/Methodology).

Enrollment for the primary endpoint evaluation is anticipated to take approximately 6-9 months. The optional extension period may take up to an additional 3 months.

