## **11.5 Monitoring Procedures**

Details will be outlined in the Study Monitoring Plan. Key risk indicators may include, but are not limited to, adverse event reporting, compliance to the protocol, enrollment, and the Investigator Site File. In the event where a particular site is not performing as expected, appropriate intervention may be made. Interventions may include, but are not limited to, retraining, site audits, enrollment suspension or site termination.

Safety monitoring on a real-time basis will be implemented, such that the sponsor, and independently the Principal Investigator, will be able to take appropriate steps to manage emergent safety signals, e.g., to put on hold or stop the clinical trial in case a safety signal is observed. In addition, an external Data Safety Monitoring Board will perform a review of the safety data after the roll-in procedures and if a safety event is triggered.

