where  $\delta_x = \nu_x + \kappa_x^2 - \kappa_x$  and  $\rho$  is the within-donor correlation in the responses over successive procedures from the same donor. The sample size involves computation of an asymptotic robust variance estimate for the estimator based on a multivariate binary probability mass function with specified marginal event rates of SHAE for the Test and Control arms and a specified exchangeable correlation for responses over successive procedures within the same donor, using the conditional linear family (Preisser and Qaqish, 2014) of multivariate binary models. In addition to the response model, a zero-truncated negative binomial model is used for the number of donation procedures over time from each donor which accommodates between-donor heterogeneity in the procedure rate. The number of required donors is computed based on the constraint

$$P \left( \hat{\beta}_1 + 1.96 \sqrt{\text{asvar}_A(\hat{\beta}_1)} < \beta_{1M} | \beta_1 = \beta_{1A} \right) = 0.80$$

which ensures that the probability that the upper limit of a two-sided 95% confidence interval for the relative risk is below  $RR_M = \exp(\beta_{1M}) = 2$  with 80% power if the true log relative rate is determined by  $\beta_{1A}$ . Based on historical data, the event rate in the control arm is expected to be 0.221% thus setting  $p_C = 0.00221$  or equivalently  $\log \mu_0 = \beta_0 = \log(0.00221)$ . The margin of non-inferiority is specified as  $\exp(\beta_{1M}) = 2$ . To accommodate a slight elevation in the SHAE rate under the alternative hypothesis of non-inferiority, the sample size calculations will be carried out with  $\exp(\beta_{1A}) = 1.2$ , corresponding to a 20% relative increase in the SHAE rate (still within the region of non-inferiority).

Accommodating a slight increase helps ensure that the power objectives are met to demonstrate non-inferiority even if there is a 20% relative increase in the SHAE rate using the Aurora Xi New Nomogram. In order to achieve 80% power when  $\exp(\beta_{1A})$  equals 1.2,

when donations are taken over an 8-week follow-up period, a sample size of  $n = 11,519$  donors may be required. The total number of procedures across all trial participants of  $n \times \kappa$  will target 51,720 for the primary endpoint evaluation.

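### Protocol 12.10 pre-specifies no severe-event trigger for DSMB review after the first half of planned procedures, including the high-risk extension

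*Protocol*

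**What the plan says.** Besides the roll-in review, Protocol 12.10 lists two criteria that bring the DSMB in.

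- Rule 1, one or more deaths: "If at any time during the study there are".
- Rule 2, "6 or more severe hypotensive events" of class 1.5 or 1.6: "If at any point in the first 50% of planned procedures, there are". No arm is named, so the count is read here as pooled.

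The text under Rule 2 sets out what follows: the DSMB is told within 24 hours of the sponsor learning of the events, it reviews them unblinded, the study may be put on hold, and the outcome goes to the FDA.

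Protocol 11.5 describes the DSMB's timing in the same way: "an external Data Safety Monitoring Board will perform a review of the safety data after the roll-in procedures and if a safety event is triggered". Neither it nor Protocol 12.6 gives a periodic meeting schedule. Protocol 12.11 covers failure of the primary endpoint, slow enrolment and sponsor discretion, and contains no severe-event criterion. SAP section 6 only points back to Protocol section 12.

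The optional extension (Protocol 5.1) starts after the procedure target has been reached and is a period "during which only donors who qualify for one or more high risk subgroup" take part. It may last up to three months.

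**The concern.** A safety rule that is followed exactly as written stops applying at the halfway point, and nothing in the protocol replaces it. With five severe events in the first half, any number of further non-fatal severe or injury events would meet neither criterion in 12.10.

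What lapses is the only written route by which a count of severe events obliges an unblinded DSMB look. The roll-in review does not fill that role, because Protocol 12.5 hides the randomization category and the collected volumes from its reviewers. The extension lies wholly beyond the halfway point, admits only the subgroups labelled high risk, and opens only if a subgroup's procedure target has been missed (Protocol 12.4.2).

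**Working it through.** **Inputs from the documents.** The procedure total "will target 51,720 for the primary endpoint evaluation" (Protocol 12.2). On donors, "It is estimated that the study will enroll approximately 11,519 subjects" (Protocol 5.1), so the mean is 51,720 / 11,519 = 4.49 procedures per donor. The control SHAE rate is 0.221% per procedure, the assumed relative rate 1.2, the margin 2, and power 80% with a two-sided 95% interval (Protocol 12.2). The Rule 2 count is 6.

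**The plan's own total.** Under the formula in Protocol 12.2 without clustering, with p0 = 0.00221 and p1 = 1.2 × 0.00221 = 0.002652:

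N = 2 × [(1 − p0)/p0 + (1 − p1)/p1] × (1.96 + 0.8416)² / (ln 2 − ln 1.2)² = 49,784.

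The stated 51,720 is 51,720 / 49,784 = 1.039 times this. That inflation corresponds to a within-donor correlation of about 0.005 to 0.009 if the variance-to-mean ratio of procedures per donor is 1 to 5. Neither quantity is stated, so the total is plausible but cannot be reproduced exactly. The point below does not depend on it.

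**Rule 2's window.** 50% of 51,720 = 25,860 procedures, and 6 / 25,860 = 2.32 per 10,000. Using 51,720 as the base is an inference, because Rule 2 does not define planned procedures. If extension procedures were counted in the base, the cut-off would move later but the rule would still lapse halfway.

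**Illustration.** The documents give no rate for class 1.5/1.6 events. I assume constant rates r of 0.5 to 4 per 10,000, which is 0.5/22.1 = 2% to 4/22.1 = 18% of the control SHAE rate. Procedures are treated as independent.

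- a = P(X ≥ 6), X binomial (25,860, r): Rule 2 fires in the first half.
- (1 − a) × a: Rule 2 stays silent, then six or more events occur in the second half alone.
- b − a, with b = P(X ≥ 6) for X binomial (51,720, r): Rule 2 stays silent, but the cumulative count reaches six by the end of the primary period.

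| r per 10,000 | Expected per half | a | (1 − a) × a | b − a |
|---|---|---|---|---|
| 0.5 | 1.29 | 0.2% | 0.2% | 4.6% |
| 1 | 2.59 | 4.8% | 4.6% | 36.6% |
| 2 | 5.17 | 41.4% | 24.3% | 53.1% |
| 3 | 7.76 | 78.6% | 16.8% | 21.2% |
| 4 | 10.34 | 94.5% | 5.2% | 5.5% |

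The fourth column is the fairer measure of the gap, since it applies the same count to the same exposure. At high rates the first half usually fires; at low rates neither half does. The gap is widest at rates near Rule 2's own implied level of 2.3 per 10,000. Extension procedures would add to the uncovered exposure but are not included, because their number is not fixed.

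**The case against.** The strongest reply is that oversight continues. Protocol 11.5 provides real-time safety monitoring under which the sponsor, and separately the Principal Investigator, can hold or stop the trial. Protocol 10.2 requires SAEs to reach the sponsor within 24 hours. Protocol 6.11 allows termination for safety at any time. Under 12.6 the DSMB meets as required, can devise its own criteria and ask for unblinded data, and its decision binds the sponsor. All of this stands, and a reader who inferred that safety monitoring ends at 50% would be wrong. But 11.5 and 12.6 state no later severe-event threshold, and 10.2 names no route from an SAE report to the DSMB. These are powers to act, not a criterion that requires action.

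The charter is not among the documents and may hold later criteria or a meeting schedule. That also stands, so the claim is limited to what the protocol pre-specifies.

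A fixed count needs a defined exposure window, because an open-ended count of six becomes easier to reach as procedures accumulate. This is fair, and limiting Rule 2 to an early phase is a recognisable choice. It argues for a different count or rate later rather than none. The windows of Rules 1 and 2 differ without contradicting each other.

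The extension is optional, follows a successful primary analysis, and draws on subgroups eligible from the start. One of these is all female donors, with a target of 26,366 procedures in SAP 4.2. A reader might infer that monitoring is weakest exactly where risk per procedure is highest. The documents label these donors high risk but give no severe-event rate for them, so that statement cannot be quantified.

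A reader might also pose a rate of 1 per 10,000 that triples at the halfway point, and contrast a 79% chance of reaching six in the second half with a 0% chance of a trigger as written. The documents do not support that as a headline. They give neither rate, and eligibility, devices and allocation are not planned to change at 50%. The protocol also has no rule restarting the count, so reaching six in the second half alone serves here only as a yardstick.

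**Conclusion.** The point holds in this form: Protocol 12.10 pre-specifies no class 1.5/1.6 trigger for DSMB review after the first 50% of planned procedures, whereas the death trigger runs throughout. The second half, about 25,860 procedures on the 51,720 base, and the whole extension have no written severe-event count or rate that requires notification and unblinded review.

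The conclusion rests on the wording alone. The size is illustrative: about 5%, 24%, 17% and 5% at assumed constant rates of 1, 2, 3 and 4 per 10,000, with independent procedures. It does not follow that these periods are unmonitored, or that a late signal could not reach the DSMB. This is a cheap improvement to a safety rule.

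**What to change.** Amend Protocol 12.10, and align the DSMB charter, so that a severe-event review criterion stays in force for the second half and for the extension. State what planned procedures means, which exposure window each criterion covers, and whether the count is cumulative or restarts. The DSMB and sponsor should set the count or rate; none is proposed here. If the charter already holds a later criterion, 12.10 should refer to it.

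The cost is a wording change to the protocol and charter, with any IRB approval it needs, and possibly one or more additional DSMB reviews. The primary analysis and the sample size are unaffected.

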## 12.11 Stopping Rules

After the primary endpoint evaluation period, the extension period, if needed, will end at the discretion of the sponsor, when a sufficient sampling of each high-risk subgroup has been achieved. Due to potential difficulty recruiting participants from each high-risk subgroup, the sponsor reserves the option to stop the study prior to or at any time during this optional extension period.

- If the primary endpoint fails, then the extension phase will not occur.
- If enrollment during the extension period for any of the subgroups is not sufficient to complete the study in a reasonable time period (up to 3 months), then the extension period could be stopped at the discretion of the sponsor.

## 13 ADMINISTRATIVE RULES

### 13.1 Investigators' Responsibilities

The study will be conducted in a manner designed to assure the acceptability of the data by regulatory authorities. All Investigators, Sub-investigators, and DSMB members are required to complete a Disclosure of Financial Interest supplied by the Sponsor. This section contains a summary of Investigator responsibilities that will help ensure the study is performed in compliance with regulations. Specific mechanisms and procedures are described to maintain the compliance of both the Investigator and the Sponsor.

The PI may delegate tasks to qualified members of the investigation site team but retains responsibility for the clinical investigation. This also applies when activities are outsourced to an external organization by the Principal Investigator, in which case he/she shall implement procedures to ensure the integrity of all tasks performed and any data generated by this external organization.

Certain events in the performance of the study require particular reports from the Investigator within prescribed time frames. A summary of the required Investigators' reports follows:

**Table 44. Required Reports from Investigator**

Report	Submit To	Time
Withdrawal of IRB approval 21 CFR 812.150(a)(2)	Sponsor	Within 5 working days
Progress Report(s) 21 CFR 812.150(a)(3)	Sponsor, Monitor, IRB	Regular intervals (at least yearly)

Report	Submit To	Time
Deviation from protocol 21 CFR 812.150(a)(4)	Sponsor, IRB	ASAP but no later than 5 working days
Failure to obtain informed consent 21 CFR 812.105(a)(5)	Sponsor, IRB	Within 5 working days
Final Report (Completed Case Report Forms constitute a Final Report from Investigator) 21 CFR 812.150(a)(6)	Sponsor, IRB	Within 3 months after termination
Both Serious and Unanticipated Adverse Device Effects 21 CFR 812.150(a)(1)	Sponsor	ASAP (within 24 hours) by telephone, facsimile or email
	IRB	ASAP, but in no event later than 10 working days after the investigator first learns of the effect.

Note: Requirements for Investigator-required reports may vary, depending on local regulatory requirements.

### **13.1.1 Confidentiality**

The Investigator and his/her staff will agree to treat all aspects of the study in a confidential manner. All documents and data pertaining to the study can only be released with the consent of the Sponsor or as required by federal or state law or authorized regulatory agencies. Each Investigator agrees to permit review of all pertinent data by the Sponsor or its agents as well as representatives of the US FDA or other appropriate regulatory agencies during and/or following performance of the study.

### **13.1.2 Protocol Modifications**

All protocol revisions must be issued by the Sponsor. The investigator will acknowledge the change by signing and dating the Investigator Signature Page. Protocol modifications should not be implemented prior to any required IRB approval, except where necessary to eliminate hazards to subjects when the change(s) involve only logistical or administrative details (example: address or telephone change).

### **13.1.3 Protocol Deviations**

In situations regarding a departure from the protocol, the investigator will contact the appropriate Sponsor representative as soon as possible but no later than 5 working days. Notification to the Sponsor should be made prior to implementing a departure from the protocol, if at all feasible. In all cases, contact with the Sponsor should be made as soon as possible in order to discuss the situation and agree on an appropriate course of action. Protocol deviation(s) will be documented and describe any departure from the protocol and the circumstances that necessitated the departure.

### **13.1.4 On-Site Audits**

The investigator agrees to allow representatives of the sponsor to visit the investigational site to carry out an audit of the study in compliance with regulatory guidelines and company policy. Such audits will require access to all study records, including source

documents, for inspection and comparison with CRFs. Subject privacy will be respected at all times and will be in accordance with any local or country-specific requirements. Sufficient prior notice will be provided by the sponsor to allow the investigator time to prepare for the audit.

The governing IRB may conduct an on-site audit during the course of the study. The investigator should notify the Sponsor if he has been contacted by the IRB regarding an audit.

Similar auditing procedures may be conducted by agents of any regulatory body reviewing the results or procedures of this study. The investigator should immediately notify the Sponsor if they are contacted by a regulatory agency concerning an inspection.

### **13.1.5 Institutional Review Board**

The Investigator will be responsible for obtaining IRB approval for the study and for providing the Federalwide Assurance (FWA) and/or Institutional Review Board Organization (IORG) number(s) to the Sponsor, as appropriate. All study-related plasma facility SOPs and work aids will be submitted to the IRB, as required. After approval of the protocol, informed consent form, and any other adjunctive material (e.g., marketing flyers) by the IRB, the investigator must provide a copy of the IRB approval document to the Sponsor. Copies of these documents are to be maintained at the study site.

The written notification must be signed by the Chairman of the IRB, or his/her designee, and must identify the specific protocol. In cases where an IRB member has a specific conflict of interest, abstention of the individual from the vote should be documented. An investigator or sub-investigator may be a member of the IRB but may not participate in the deliberation or vote on any research in which he/she is involved.

